#### 10.2.1.2. Serious Adverse Event (SAE)

An AE is considered "serious" if, in the view of either the Investigator or Capricor, it results in any of the following outcomes:

- Death
- Life-threatening adverse event
- Inpatient hospitalization or prolongation of existing hospitalization
- Persistent or significant incapacity or substantial disruption of the ability to conduct normal life functions
- Congenital anomaly/birth defect

Important medical events that may not result in death, be life-threatening, or require hospitalization may be considered serious when, based upon appropriate medical judgment, they may jeopardize the subject and may require medical or surgical intervention to prevent one of the outcomes listed in this definition.

Examples of such medical events include bronchospasm requiring intensive treatment in an emergency room or at home, blood dyscrasias, or convulsions that do not result in inpatient hospitalization, or the development of drug dependency or drug abuse.

Complications that occur during a hospitalization are AEs. When the hospitalization is prolonged due to the complication or the complication fulfills any other serious criteria, the event is reported as an SAE. Hospitalization for elective treatment of a pre-existing condition that did not worsen from baseline is not considered an SAE.

Page 48 of 78 Capricor, Inc. - Company Confidential

#### 10.2.1.3. Expected Adverse Events

As deramiocel is comprised of allogeneic cells, immunologic reactions to the product are a possible AE. In the completed randomized, double-blind, placebo-controlled HOPE-2 and open-label HOPE-OLE trials, 3 allergic reactions assessed as related to IP were reported as SAEs for 3 subjects. Allergic reactions during or after an infusion of cell products have been reported and can be prevented or mitigated by specific pre-treatment regimens, which were implemented in the HOPE-2 trial after these reactions occurred. A total of 42 deramiocel or placebo infusions were administered in the HOPE-2 trial after the introduction of the pre-treatment regimen and a single allergic reaction was reported. This subject experienced a likely allergic reaction requiring overnight observation during his third IV administration of IP, the event was assessed as not life-threatening. All 3 subjects that experienced an allergic reaction were observed overnight and discharged without any sequelae on the following day.

Other risks of the infusion procedure include those risks that are possible with the intravenous administration. These include risks related to infection, bleeding, pain, bruising and/or hematoma at the vascular access site(s).

#### 10.2.1.4. Unexpected Adverse Events

An AE is considered "unexpected" if it is not listed in the Investigator's Brochure or is not listed at the specificity or severity that has been observed, if the Investigator's Brochure is not required or available, or if it is not consistent with the risk information described in the general investigational plan or elsewhere in the current application.

"Unexpected," as used in this definition, also refers to adverse events or suspected adverse reactions that are mentioned in the Investigator's Brochure as occurring with a class of drugs or as anticipated from the pharmacological properties of the drug, but are not specifically mentioned as occurring with the particular drug under investigation.

Expedited reporting is required for serious unexpected AEs as discussed in Section 10.2.4.

#### 10.2.1.5. Other Adverse Event (OAE)

OAEs will be identified by the Medical Monitor during the evaluation of safety data for the Clinical Study Report. Significant adverse events of particular clinical importance, other than SAEs and those AEs leading to discontinuation of the subject from the trial, will be classified as OAEs.

For each OAE, a narrative may be written and included in the Clinical Study Report.

#### 10.2.2. Relationship to Investigational Product

The Investigator will assess the relationship (causality) of an AE to the investigational product and administration procedure.

Causality will be defined as follows:

• *Probable*: adverse events that, after careful medical evaluation, are considered with a high degree of certainty to be related to the investigational product or administration procedure. The following characteristics will apply:

- A reasonable temporal relationship exists between the event and the investigational product or administration procedure, and
- The event is a known reaction to the investigational product or administration procedure, which cannot be explained by an alternative etiology commonly occurring in the population/individual.
- *Possible*: adverse events that, after careful medical evaluation, do not meet the criteria for a probable relationship to the investigational product or administration procedure, but for which a connection has reasonable certainty. The following characteristics apply:
  - The event occurs after exposure to the investigational product or administration procedure, and
  - The event is not a known reaction to the investigational product or administration procedure, but cannot be explained by a commonly occurring alternative etiology, or
  - In the absence of a temporal relationship, the event cannot reasonably be explained by an alternative etiology.
- *Unlikely*: adverse events that, after careful medical evaluation, do not meet the criteria for possible or probable relationship to investigational product or administration procedure and for which a connection is unlikely. The following characteristics will apply:
  - The event does not follow a reasonable temporal sequence from administration of the investigational product or administration procedure, or
  - May be explained by commonly occurring alternative etiology in the population/individual, or
  - May have been produced by environmental factors, and there is no apparent pattern of response to the investigational product or administration procedure.

An adverse event will be reported as "related" when causality is evaluated by an Investigator as probably or possibly related to the investigational product and/or the administration procedure. Related adverse events indicate a potential cause-and-effect relationship between the investigational product and/or administration procedure and the occurrence of the adverse event.

An adverse event will be reported as "unrelated" when causality is evaluated by an Investigator as unlikely related to the investigational product and/or administration procedure by the Investigator. Unrelated adverse events indicate no relationship between the occurrence of the adverse event and the investigational product and/or administration procedure.

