For trials conducted under an investigational new drug (IND) application, FDA regulations require reporting of any serious suspected adverse reaction that is unexpected according to the current Investigator's Brochure. A serious adverse reaction is defined as any adverse event for which there is a reasonable possibility that the drug/biologic caused the AE. For the purposes of IND safety reporting, "reasonable possibility" means there is evidence to suggest a causal relationship between the drug/biologic and the adverse event. Serious, unexpected suspected adverse reactions (SUSARs) are SAEs that are unexpected and are possibly or probably related to participation in the research. Expedited reporting is required for all SUSARs. Capricor will send an IND Safety Report to the FDA within 7 calendar days of receipt for fatal/life-threatening events, and within 15 calendar days of receipt for non-fatal/non-life-threatening events that qualify for expedited reporting.

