### 7.1 Adverse Events

AEs will be coded using MedDRA coding system (Version 23.1).

The following AEs are defined as TEAEs:

- AEs that occur after the initiation of the IV catheter placement for the initial dose of IP
- AEs with a completely missing start date, or similarly, AEs that start the same month and year as IP administration but that have a missing start day.

TEAEs are considered to be related to IP/administration procedure if the relationship of the particular event is marked as "possible" or "probable".

Subject listings of all AEs as reported will be provided. Serious AEs and TEAEs that are assessed as related to the IP or administration procedure, and hypersensitivity reactions/acute respiratory decompensation will be listed separately.

All summary tables will be reported using TEAEs. Additionally, TEAEs by maximum severity and TEAEs that are related to the IP or administration procedure and hypersensitivity reactions/acute respiratory decompensation will be summarized.

TEAEs will be displayed by MedDRA SOC and PT, with subjects who experience the same TEAE counted only once for that event and subjects who have more than one TEAE within a SOC counted only once in that SOC. The numbers and percentages of subjects with an event, as well as the number of events that were reported, will be calculated.

The summary tables will be prepared first for 12 months from the date of first IP administration during the OLE Phase and then again through 60 months in the OLE Phase.

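### Protocol 10.2.2: a well-timed known reaction with a commonly occurring alternative cause meets neither Probable nor Possible, so it cannot be counted as related

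*Protocol*

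**What the plan says.** Protocol 10.2.2 defines three causality categories.

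- **Probable** requires a reasonable temporal relationship and a known reaction "which cannot be explained by an alternative etiology commonly occurring in the population/individual".
- **Possible** requires that the event follow exposure and that one of two further conditions hold. The first is "The event is not a known reaction to the investigational product or administration procedure, but cannot be explained by a commonly occurring alternative etiology". The second is "In the absence of a temporal relationship, the event cannot reasonably be explained by an alternative etiology".
- **Unlikely** is for events that meet neither definition above and "for which a connection is unlikely". Three characteristics follow, joined by *or*: the timing does not fit; "May be explained by commonly occurring alternative etiology in the population/individual, or" environmental factors with no apparent pattern of response.

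Probable and Possible are reported as related and Unlikely as unrelated, with this gloss: "Unrelated adverse events indicate no relationship between the occurrence of the adverse event and the investigational product and/or administration procedure".

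SAP 7.1 uses the same split: "TEAEs are considered to be related to IP/administration procedure if the relationship of the particular event is marked as" possible or probable.

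Protocol 10.2.4 states: "Serious, unexpected suspected adverse reactions (SUSARs) are SAEs that are unexpected and are possibly or probably related to participation in the research". The same section bases the sponsor's duty to report to the FDA on a reasonable possibility of causation, which it explains as evidence suggesting a causal relationship.

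**The concern.** Every subject receives deramiocel, and the external comparators in SAP 6.4 serve PUL 2.0 and cardiac MRI only. Attribution of adverse events therefore rests largely on the investigator's causality mark.

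Protocol 10.2.1.3 names the recognised reactions: immunologic and allergic reactions, and infection, bleeding, pain, bruising or haematoma at the access site. For some of these an ordinary competing explanation may be available. If such an explanation alone bars the event from both related categories, the related-event tables and listings lean towards unrelated.

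Expedited reporting is touched in a narrower set. A known reaction counts as unexpected under Protocol 10.2.1.4 when its severity or specificity differs from the Investigator's Brochure. If it is also serious, it needs a Possible or Probable mark to meet the SUSAR definition. A strict classification would then feed a reporting test that the protocol itself words more broadly.

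**Working it through.** The plan gives no figure to reproduce, so the check is a logical one on the wording of Protocol 10.2.2.

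**Inputs.** T = reasonable temporal relationship. K = known reaction. C = a commonly occurring alternative etiology could explain the event. U = some other, less common alternative. Exposure is taken as present.

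**Rules as written.**

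- Probable = T and K and not C
- Possible = not Probable, and [(not K and not C) or (not T and not C and not U)]
- Related = Probable or Possible

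Every route to related contains *not C*. Once a commonly occurring alternative exists, neither good timing nor being a recognised reaction can make the event related.

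| Event | Probable | Possible, first route | Possible, second route |
|---|---|---|---|
| T, K, C | fails: C | fails: K and C | fails: T and C |
| T, not K, C | fails: not K, C | fails: C | fails: T and C |
| T, K, U but not C | met | – | – |
| T, not K, not C | fails: not K | met | – |

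**Enumeration.** Adding two attributes used by Unlikely (environmental factor, pattern of response) gives six yes/no attributes and 2^6 = 64 combinations. On the plain reading they divide as Probable 8, Possible 20, Unlikely 36 (8 + 20 + 36 = 64). The case T, K, C fills 2^3 = 8 of them:

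| Reading of Unlikely | The 8 combinations with T, K, C |
|---|---|
| Plain: any one bullet suffices | 8 Unlikely |
| Lead-in (connection unlikely) binding and not met | 8 with no category |
| The no-pattern phrase qualifies all three bullets, lead-in not binding | 4 Unlikely, 4 with no category |

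None of the 8 is Probable or Possible on any reading. The 8 combinations with T, not K, C are not related either (all 8 Unlikely on the plain reading). These are logical combinations, not event counts or probabilities.

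**Partial repairs do not close the gap.** Deleting the not-a-known-reaction condition alone leaves the first route requiring *not C*, so T, K, C still fails. Adding a route only for T, K, C changes Possible to 20 + 8 = 28 and Unlikely to 36 − 8 = 28, but on the plain reading the 8 combinations with T, not K, C stay Unlikely.

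**The case against.** The best defence is that these are guides to judgement after careful medical evaluation, and that Unlikely applies only where the investigator finds a connection unlikely. That stands in part: such an event need not become Unlikely. The strict alternative, however, is no category at all, and it still cannot be marked as related.

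The second defence is that little depends on the mark. This is largely right.

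- The primary and secondary safety endpoints (Protocol 6.2.1 and 6.2.2) count all treatment-emergent events.
- SAP 7.1 lists and summarises hypersensitivity reactions and acute respiratory decompensation separately.
- Protocol 10.2.4 sends all SAEs to the sponsor, IRB and DSMB whatever their causality. Its reasonable-possibility commitment is not expressly tied to the investigator's mark.
- A known reaction is usually expected, so few would reach the SUSAR question.

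Three stronger readings are tempting but not supported.

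- *Any conceivable alternative defeats relatedness.* The text requires a commonly occurring alternative. With only a less common one, a well-timed known reaction stays Probable.
- *Cardiac and respiratory events can never be Possible, because every subject has DMD.* The alternative must explain the particular event. Protocol 10.2.1.1 also excludes expected disease progression from adverse events unless it is more severe than expected, so an event recorded for that reason may not be explained by DMD.
- *Related incidence is understated by 7.7 percentage points.* That is 1/13, the effect of moving one subject who has no other related event. It is not an estimate.

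**Conclusion.** The gap is real. As written, Protocol 10.2.2 keeps any temporally related event with a commonly occurring alternative out of both related categories, including a recognised reaction to the product or procedure. I found no other text in either document that repairs this.

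The consequence is confined to the related-event tables and listings in SAP 7.1 and to the SUSAR definition for serious events that are unexpected, including known reactions of unexpected severity or specificity. The direction is towards too few related events. The size cannot be computed, because the documents give neither a related-event rate nor the frequency of such competing causes.

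The conclusion assumes that investigators apply the written definitions. If some depart from them on judgement, the undercount shrinks and classification may vary between sites.

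**What to change.** Reword the two lower categories so that together with Probable they cover every event and match the reasonable-possibility test in Protocol 10.2.4.

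- **Possible:** a plausible temporal relationship, and a contribution of the product or procedure cannot reasonably be excluded, whether or not the reaction is known and even if an alternative cause exists. The existing route for events without a temporal relationship may stay.
- **Unlikely:** the event does not qualify as Possible because there is no plausible temporal relationship, or because an alternative cause is clearly more likely than the product or procedure. That an alternative merely may explain the event is no longer enough.

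Apply the wording prospectively, with a CRF completion guideline. A re-review of past events is optional. If done, it should cover all causality categories within a window fixed in advance and report both the original and the revised classification. Reviewing only Unlikely events could move marks in one direction only, which would add its own bias.

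The cost is a protocol wording change and CRF guidance, plus any re-review, which would involve 13 subjects. The related-event count may rise slightly.

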#### 10.2.3. Recording Adverse Events

Investigators will monitor all subjects for AEs during the trial and establish a diagnosis for an event based on signs, symptoms, and/or other clinical information. It is important to distinguish that individual signs and symptoms of the event are not adverse events and should not be reported.

For each AE, the Investigator will evaluate the causality and severity, report the action taken and event outcome and disclose whether or not it caused the subject to discontinue trial participation.

The following severity scale will be used as a guideline to differentiate the severity of adverse events:

- **Mild (Grade 1)**: Transient or mild discomfort; no limitation in activity; no medical intervention/therapy required
- **Moderate (Grade 2)**: Mild to moderate limitation in activity some assistance may be needed; no or minimal medical intervention/therapy required
- Severe (Grade 3): Marked limitation in activity, some assistance usually required; medical intervention/therapy required and often requiring hospitalization or prolongation of hospitalization
- Life-Threatening or Disabling (Grade 4): Extreme limitation in activity, significant assistance required; significant medical intervention/therapy required; hospitalization, prolongation of hospitalization, or hospice care
- Fatal (Grade 5)

An AE that is assessed as severe should not be confused with an SAE. Severity is a category utilized for rating the intensity of an event. An event is described as "serious" when it meets one of the pre-defined outcomes noted in Section 10.2.1.2. Both an AE and SAE can be assessed as severe. However, an AE of severe intensity may not meet SAE definition requirements.

## 10.2.4. Reporting Adverse Events

All adverse events are collected from the time of signing informed consent for trial participation until completion of the Month 60 visit or early termination, whichever occurs first. All AEs occurring after the initiation of the IV catheter placement for the initial dose of deramiocel will be considered treatment emergent. Any ongoing adverse event that has not been resolved at the time of trial completion or early termination for a subject will be marked as ongoing on the adverse event case report form (CRF).

All AEs will be entered into the electronic data capture (EDC) system by trained site personnel at the investigative site.

Expected and unexpected SAEs must be reported to Capricor and entered into the EDC system within 24 hours of discovery of the event. For events that do not have complete information available at the time of initial report, the investigative site will submit all available information at the time of the submission. All SAE Report Forms must be signed by an Investigator and submitted with available source documentation. All source documentation must be de-identified prior to submission.

All SAEs must be reported to the respective IRB in accordance with the investigative site's policies. Copies of the submission will be collected by Capricor.

All SAEs will be reported to the DSMB at least semi-annually, or more frequently at the discretion of the Medical Monitor.

Capricor will promptly upon discovery, report serious and unexpected adverse events for which there is a reasonable possibility that the investigative therapy (i.e. administration product and/or investigative product) caused the events, to the Food and Drug Administration (FDA) in accordance with 21 CFR 312.32 regulations and ICH E2A guidelines.

For trials conducted under an investigational new drug (IND) application, FDA regulations require reporting of any serious suspected adverse reaction that is unexpected according to the current Investigator's Brochure. A serious adverse reaction is defined as any adverse event for which there is a reasonable possibility that the drug/biologic caused the AE. For the purposes of IND safety reporting, "reasonable possibility" means there is evidence to suggest a causal relationship between the drug/biologic and the adverse event. Serious, unexpected suspected adverse reactions (SUSARs) are SAEs that are unexpected and are possibly or probably related to participation in the research. Expedited reporting is required for all SUSARs. Capricor will send an IND Safety Report to the FDA within 7 calendar days of receipt for fatal/life-threatening events, and within 15 calendar days of receipt for non-fatal/non-life-threatening events that qualify for expedited reporting.

#### 10.2.5. Pregnancy Reporting

It is unknown if deramiocel could affect a baby. If the partner is able to become pregnant, one or both of the partners must use some form of effective birth control. Should a female be impregnated by a trial subject, investigative sites are required to notify Capricor within 24 hours of learning about the pregnancy. The investigative site will receive the Pregnancy Reporting Form to complete and submit to Capricor, or its designee.

All pregnancies will be followed until the pregnancy outcome is known. In addition, pregnancies that are ongoing at the time of trial completion will be followed until the outcome is known. The investigative site is responsible for outcome reporting via the Pregnancy Reporting Form, including spontaneous or voluntary termination, details of birth, and the presence or absence of any birth defects, congenital abnormalities, or maternal and newborn complications.

The pregnancy is not an adverse event for the male subject unless there is a suspicion that the investigational product interfered with the effectiveness of a contraceptive medication.

#### 10.2.6. Adverse Event Follow-up

All AEs are followed by the investigative site until an outcome is known or the subject's participation in the trial concludes at either the Month 60 visit or early termination, whichever occurs first.

The investigative site is expected to review all ongoing AEs at each visit. AEs are followed until resolution or until no further changes in the event are expected (i.e., the point at which a subject experiencing an AE is treated successfully and stabilized even though he may continue to experience lingering sequelae that may never resolve), or it is agreed that further follow-up of the event is not warranted (e.g., non-serious, IP unrelated, ongoing at final visit). See Section 10.2.3 for reporting ongoing AEs at the end of trial participation.

For SAEs that were incomplete or ongoing at the time of initial submission, the investigative site is required to submit follow-up SAE Report Forms when event information is available to the research site personnel and/or an outcome is known.

